8.2.4. Additional Analyses of Mortality

Analyses of mortality will be performed in the mITT and the As Treated analysis populations and at Day 15 ([Table 67](#) and [Table 68](#)). As a supplemental analysis, a Cox model will be fit with binary indicators for treatment group and actual baseline ordinal score as well as a treatment * actual baseline ordinal score interaction term. The model will be fit in the mITT and As Treated analysis populations ([Table 74](#)). The treatment group hazard ratios and CIs and the interaction term p-value will be reported. Finally, the results of the subgroup and sensitivity time-to event analyses described in Section [6.4](#) will be presented in a table. A restricted mean survival time analysis of mortality will be performed as an exploratory analysis. The restricted mean mortality time estimates will be provided for each treatment group and randomized actual baseline ordinal score stratum as well as the difference in restricted mean recovery time between treatment groups within each of the baseline ordinal score strata ([Table 75](#)).

8.2.5. Additional Analyses of Time-to-Recovery

The analysis of Time-to-Recovery will be repeated in the mITT population but including only subjects with actual baseline Clinical Status scores in ordinal score 5 or 6 (excluding those with any other baseline score) and in the As-Treated population. The analysis will also be repeated using the Modified Recovery ordinal scale described in Section [4.3](#) ([Table 29](#)).

Sensitivity analyses will be performed using Cox proportional hazards models to estimate the hazard ratio ([Table 29](#)). First, a mITT analysis will be performed in which subjects who die prior to recovering are treated as experiencing a competing risk in the Fine-Gray proportional hazards regression model. Second, a Cox

model will be fit with binary indicators for treatment group and baseline ordinal score (5 or 6) as well as a treatment * baseline ordinal score (as a continuous variable) interaction terms. The models will be fit to the mITT analysis population. The treatment group hazard ratios and CIs will be reported for both sets of models and the interaction term p-value will be reported for the interaction models. The tabular summary will also include results from an analysis of time to recovery controlling for age and duration of symptoms as continuous covariates and baseline d-dimer and CRP values as continuous covariates.

The time-to-recovery analysis will also be repeated using the other subgroups defined in Section 6.4 in place of actual baseline ordinal score. Each subgroup will be considered separately, and the tabular and graphical summaries described in the previous section will be replicated for each subgroup. Forest plots (Figure 18 and Figure 19) will be generated to display the overall treatment hazard ratio estimate and CI from each of the within-subgroup analyses (Table 30).

As noted in Section 6.4, analyses that take into account concomitant medication will be performed (Table 32). An additional sensitivity analysis will evaluate the effect of recoveries that were not sustained as indicated in Section 3.3.2 (Table 31).

A restricted mean survival time analysis will be performed as an exploratory analysis. The restricted mean recovery time estimates will be provided for each treatment group and actual baseline ordinal score stratum as well as the difference in restricted mean recovery time between treatment groups within each of the baseline ordinal score strata (Table 34).

Two corroborative summaries will also be generated. A summary of the number and percentage of subjects in each treatment group who recovered (and are alive), did not recover (and are alive), and died by Day 29 will be summarized. The summary will also include the numbers and percentages, grouping deaths and non-recoveries together (Table 35). The summaries will also be provided by the Modified Recovery ordinal scale (Table 33) and the duration of symptoms categorizations specified in Section 6.4.

Other censoring techniques and additional analyses of the primary outcome may be performed.

8.2.6. Time-to Improvement in Clinical Status

Time to improvement by at least one category in the clinical status 8-point scale (see Section 3.3). The log rank test will be performed using a Cox proportional hazards model to test whether the curves differ between treatment arms. The median time to event and CI in each treatment group will be summarized along with the treatment hazard ratio estimate and log rank p-value (Table 36). Differences in time-to-event endpoints by treatment arm will be summarized with Kaplan-Meier curves (Figure 14). Number at risk, hazard ratio and log rank p-values will be presented on the figures. The analyses (and tabular and graphical summaries) will be repeated using the outcome of time to improvement in two categories of the ordinal scale defined in Section 3.3.

The above analyses will be repeated with the modification to the ordinal scale described in Section 4.3 (Table 37). The only subgroup analysis that will be performed for time to improvement will be an analysis that classifies subjects by the duration of symptoms at baseline subgroups (above/below the median) (Table 38).

8.2.7. Clinical Status Ordinal Scale While Hospitalized, Day 22, Day 29

The number and proportion of subjects along with 95% confidence intervals by category of clinical status will be presented by treatment arm at Study Visit (not necessarily actual) Days 1, 3, 5, 8, 11, 15 and 29 (Table 39).

Change from baseline will also be summarized at Days 3, 5, 8, 11, 15, 22, and 29 ([Table 39](#)) and by subgroup ([Table 40](#)). Individual subject listings of clinical status scores will be presented ([Listing 5](#)).

8.2.8. Desirability of Outcomes Response (DOOR)

Proportions of subjects in each category of DOOR response (1 through 7) and 95% confidence intervals will be presented by treatment arm at Study Visit 15 and 29 ([Table 41](#)) in the mITT population. DOOR score will be summarized at Day 3, 5, 8, 11, 15, 22, and 29 mITT population ([Table 42](#)). The treatment arms will be compared at Day 15 and Day 29 using a Mann-Whitney U-statistic. Additionally, the mean DOOR score by Day and treatment group will be displayed in [Figure 20](#). Individual subject listings of DOOR scores will be presented ([Listing 6](#)).

8.2.9. Days of Oxygenation

Duration of oxygenation use will be summarized in a table using means, standard deviations, medians and quartiles by treatment arm ([Table 43](#)). Analyses will be performed in the mITT and As Treated populations, and by duration of symptoms at baseline ([Table 44](#)). Bee swarm plots of oxygen days by treatment arm will be generated, where subjects whose days are imputed to the maximum of 28 days due to death are grouped separately from subjects who do not die ([Figure 21](#)).

8.2.10. Incidence of New Oxygen Use

The incidence and duration of new oxygen use will be analyzed by treatment arm. This will only include subjects in category 4 at randomization. New use will be identified by a post-randomization score of at least 5; the number of subjects reporting new use and the incidence rate (and CI) will be reported ([Table 43](#)).

8.2.11. Days of Non-Invasive Ventilation/High-Flow Oxygen

Duration of non-invasive ventilation/high flow oxygen use will be summarized in a table using means, standard deviations, medians, and quartiles by treatment arm ([Table 45](#)). Analyses will be performed in the mITT and As Treated populations and by duration of symptoms at baseline ([Table 46](#)). Bee swarm plots of non-invasive ventilation/high flow oxygen days by treatment arm will be generated, where subjects whose days are imputed to the maximum of 28 days due to death are grouped separately from subjects who do not die ([Figure 22](#)).

8.2.12. Incidence of New Non-Invasive Ventilation/High-Flow Oxygen

The incidence and duration of new Non-Invasive Ventilation/High-Flow Oxygen use will be analyzed by treatment arm. This will only include subjects in category 5 or 6 at randomization. New use will be identified by a post-randomization score of 6. The number of subjects reporting new use and the incidence rate (and CI) will be reported ([Table 45](#)).

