3.3.4. Clinical Status Ordinal Score at Specific Timepoints

The Primary Endpoint, Key Secondary Endpoint, and several other Secondary Endpoints rely on evaluation of the Clinical Status ordinal score at specific days. For these endpoints, the Study Visit Day is the timepoint of interest, not the actual study day (e.g., Study Visit Day 29 as opposed to study day 29). The Clinical Status Score collected at the Study Visit corresponding to the specific endpoint will be used for the outcome. Specifically, results from Study Visit Day 29 will be used for the Primary Endpoint and results from Study Visit Day 15 will be used for the Key Secondary Endpoint, with these and other Study Visit Days (3, 5, 8, 11, 22) used for other Secondary Endpoints. For analyses involving Clinical Status at specific timepoints, imputation of missing scores may be performed following the rules described in Section 6.5.

3.3.5. Progression to Clinical Status Category 6, 7, or 8 by Day 29

This Secondary Endpoint will be assessed similarly to Mechanical Ventilation-free survival (Section 3.3.2), but the event of interest is any report of a Clinical Status ordinal score in Category 8 (Death), Category 7 (invasive mechanical ventilation or ECMO), or Category 6 (non-invasive ventilation or high-flow oxygen device). This endpoint will only be assessed in those with actual baseline Clinical Status in Category 5 (hospitalized, requiring supplement oxygen).

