4.2.3. Method of Assigning Subjects to Treatment Groups (Randomization)

Randomization will be stratified by:

- Site
- Clinical Status at enrollment (by ordinal scale)
 - Category 6: Hospitalized, on non-invasive ventilation or high flow oxygen devices, OR
 - Category 5: Hospitalized, requiring supplemental oxygen

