4.3. Efficacy and Safety Variables

For each study day while the patient is hospitalized, the clinical status will be recorded on an 8-point ordinal scale as follows:

- Day 1 – The clinical assessment at the time of randomization.
- Day 2+ - The most severe assessment occurring from midnight to midnight (00:00 to 23:59) of the prior day (e.g., the value recorded on Day 3 will be the most severe outcome that occurred on Day 2).

where the clinical status scale is defined as follows:

Category 8: Death;

Category 7: Hospitalized, on invasive mechanical ventilation or ECMO;

- Category 6: Hospitalized, on non-invasive ventilation or high flow oxygen devices;
- Category 5: Hospitalized, requiring supplemental oxygen;
- Category 4: Hospitalized, not requiring supplemental oxygen - requiring ongoing medical care (COVID-19 related or otherwise);
- Category 3: Hospitalized, not requiring supplemental oxygen - no longer requiring ongoing medical care. This would include those kept in hospital for quarantine/infection control, awaiting bed in rehabilitation facility or homecare, etc.;
- Category 2: Not hospitalized, but has new or increased limitation on activities and/or new or increased requirement for home oxygen over baseline, pre-COVID-19 status;
- Category 1: Not hospitalized, patient is back to their baseline, pre-COVID-19 status, that is, no new or increased limitations on activities and no new or increased oxygen use compared with baseline.

A modified version of the ordinal scale will be used in sensitivity analyses of the Key Secondary and Other Secondary Endpoints of time-to-recovery and time-to-improvement.

The “Modified Recovery” ordinal scale combines Category 1 and 3 of the original Clinical Status scale and is defined as follows:

- Category 8: Death;
- Category 7: Hospitalized, on invasive mechanical ventilation or ECMO;
- Category 6: Hospitalized, on non-invasive ventilation or high flow oxygen devices;
- Category 5: Hospitalized, requiring supplemental oxygen;
- Category 4: Hospitalized, not requiring supplemental oxygen - requiring ongoing medical care (COVID-19 related or otherwise);
- Category 3: Not hospitalized, but new or increased limitation on activities and/or requiring new or increased home oxygen;
- Category 2: Hospitalized, not requiring supplemental oxygen - no longer requires ongoing medical care; or Not hospitalized, no limitations on activities.

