Days of Oxygen (Among subjects who did not die)	N		x	x
	Mean (SD)		x.x (x.x)	x.x (x.x)
	Q1		x.x	x.x
	Median		x.x	x.x
	Q3		x.x	x.x
	Difference in Medians (95% CI)		x.x (x.x, x.x)	
Not on Oxygen at Baseline (N = x)				
New Oxygen Use	N		x	x
	n		x	x
	Incidence Rate		x.x	x.x
	Incidence Rate 95% CI		x.x, x.x	x.x, x.x
	Difference in Rates (95% CI)		x.x (x.x, x.x)	
Days on Oxygen (Including imputations for subjects who died)	N		x	x
	Mean (SD)		x.x (x.x)	x.x (x.x)
	Q1		x.x	x.x
	Median		x.x	x.x
	Q3		x.x	x.x
	Difference in Medians (95% CI)		x.x (x.x, x.x)	
Days of Oxygen (Among subjects who did not die)	N		x	x
	Mean (SD)		x.x (x.x)	x.x (x.x)
	Q1		x.x	x.x
	Median		x.x	x.x
	Q3		x.x	x.x
	Difference in Medians (95% CI)		x.x (x.x, x.x)	
Repeat for As Treated Population.				

N = Number of subjects in the specified analysis population and oxygen use category.
Q1 and Q3 are the first and third quartiles, respectively.

Programming Note: For the “Days on Oxygen” statistics within the “Not on Oxygen at Baseline” subgroup, only summarize days for subjects who reported new use.

Tables with similar format:

Table 44: Oxygen Use Through Day 29 by Treatment Group and Duration of Symptoms at Baseline – Actual Baseline Ordinal Score of 5 or 6

Table 45: Non-invasive Ventilation/High-Flow Oxygen Use Through Day 29 by Treatment Group – Actual Baseline Ordinal Score of 5 or 6

Table 46: Non-invasive Ventilation/High-Flow Oxygen Use Through Day 29 by Treatment Group and Duration of Symptoms at Baseline – Actual Baseline Ordinal Score of 5 or 6

Table 47: Ventilation/ECMO Use Through Day 29 by Treatment Group – Actual Baseline Ordinal Score of 5 or 6

Table 48: Ventilation/ECMO Use Through Day 29 by Treatment Group and Duration of Symptoms at Baseline – Actual Baseline Ordinal Score of 5 or 6

Programming notes for Table 44, Table 46, and Table 48:

“Analysis Population” will be replaced by “Duration of Symptoms at Baseline” column. The tables will consider the duration above/below median subgroup. Summaries will only be generated for mITT population.

Programming notes for Table 47, Table 48:

The “On Ventilation/ECMO at Baseline” section of the table will not be generated.

Programming notes for Table 43 and Table 44:

The “New Use” section of the table will not be generated.

Programming notes for Tables 43, 44, 45, 46, 47, 48

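### Section 8.2.12 counts subjects already on non-invasive ventilation or high-flow oxygen as new users, which contradicts the parallel rules and the Table 45 shell

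*SAP*

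**What the plan says.** Section 8.2.12 plans the incidence and duration of new NIV/high-flow use by arm, reported in Table 45. On the population: "This will only include subjects in category 5 or 6 at randomization". On the event: "New use will be identified by a post-randomization score of 6". It does not require a score below 6 first.

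Section 4.2.3 defines one of the two randomization strata as "Category 6: Hospitalized, on non-invasive ventilation or high flow oxygen devices, OR" the other being category 5. Section 4.3 sets the daily scoring rule: "Day 2+ - The most severe assessment occurring from midnight to midnight (00:00 to 23:59) of the prior day".

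Two neighbouring rules restrict the population to subjects not yet on the support in question:

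- Section 8.2.10, new oxygen use: "This will only include subjects in category 4 at randomization".
- Section 3.3.5, progression to category 6, 7 or 8: "This endpoint will only be assessed in those with actual baseline Clinical Status in Category 5".

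Table 45 is listed in Appendix 1 as having the same format as Table 43. The Table 43 shell has one block for subjects on the support at baseline, showing days only. A second block (headed "Not on Oxygen at Baseline (N = x") holds the new-use count, incidence rate and rate difference. A programming note limits the days in that second block to subjects with new use. Further notes drop the new-use rows for Tables 43 and 44 only, and the on-support block for Tables 47 and 48 only. Table 45 therefore keeps both blocks.

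**The concern.** A subject in category 6 at randomization is on NIV or high-flow oxygen already. Because the Day 2 record carries the worst status of Day 1, that subject will almost always have a post-randomization 6 with nothing new having happened. The main exception is a subject who goes straight to category 7 or dies.

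The restriction in Section 8.2.12 also excludes almost nobody. Categories 5 and 6 are the two strata, and Section 15.3 reports one known subject who was neither. A restriction meant to remove existing users therefore leaves them in.

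Incidence and duration of new NIV/high-flow use is a listed secondary objective (Section 3.1). Under the text, its incidence mixes new use in category 5 with continuing use in category 6, and the contrast between arms is diluted. A programmer working from Section 8.2.12 and one working from the Table 45 shell would report different numbers under the same label.

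**Working it through.** The SAP states no incidence, effect size or category 6 share for this endpoint, so it has no figure to reproduce. The comparison below is algebra plus a labelled illustration.

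**Inputs**

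- q: share of subjects starting in category 6. Not in the SAP; assumed 15% to 35%.
- s: chance that a baseline-6 subject scores 6 again after randomization. Close to 1 by the Section 4.3 scoring rule; taken as 1.
- p: true new-use risk in baseline category 5. Not in the SAP; assumed 20% in one arm and 15% in the other.

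**Formulas under the Section 8.2.12 text**

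- Counted incidence = q·s + (1 − q)·p.
- Risk difference, with s equal in both arms = (1 − q) × (difference in p), because the q·s term cancels.
- Share of counted cases already on support at baseline = q·s / [q·s + (1 − q)·p].

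**Results with s = 1**

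| | Category 5 only | Text, q = 0.15 | Text, q = 0.35 |
|---|---|---|---|
| Incidence, p = 0.20 | 0.20 | 0.15 + 0.85 × 0.20 = 0.320 | 0.35 + 0.65 × 0.20 = 0.480 |
| Incidence, p = 0.15 | 0.15 | 0.15 + 0.85 × 0.15 = 0.2775 | 0.35 + 0.65 × 0.15 = 0.4475 |
| Risk difference | 0.050 | 0.0425 | 0.0325 |
| Risk ratio | 0.75 | 0.87 | 0.93 |
| Already on support, p = 0.20 arm | 0 | 0.15/0.320 = 47% | 0.35/0.480 = 73% |
| Already on support, p = 0.15 arm | 0 | 0.15/0.2775 = 54% | 0.35/0.4475 = 78% |

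Taking s = 0.95 changes little: the risk ratios become 0.270/0.3125 = 0.86 and 0.430/0.4625 = 0.93.

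**When existing users exceed half of the counted cases.** With s = 1 this needs q > p/(1 + p): 13% for p = 0.15, 17% for p = 0.20, 23% for p = 0.30 and 29% for p = 0.40. Over q from 0.1 to 0.5 and p from 0.10 to 0.40, the share runs from 0.1/0.46 = 22% to 0.5/0.55 = 91%.

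**Under the Table 45 shell.** New use is counted only among subjects not on NIV/high-flow at baseline, which in this trial means category 5. The incidence equals p, the share already on support is 0, and nothing is diluted.

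**The case against.** The strongest reply is that the shell already does the right thing. Table 45 in the Table 43 format separates the two groups, puts new use only in the not-on-support block, and limits days there to new users. Section 6.4 also plans all secondary outcomes by actual baseline score, which would yield a category 5 figure. The closely related question of escalation from category 5 has its own correctly restricted endpoint (Sections 3.3.5 and 8.1.2.2) inside the fixed sequence.

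Much of this stands. A reader might infer from Section 8.2.12 that the reported incidence will be mainly existing use, or that days of new use will be dominated by continuing use. The documents support neither as fact. The first depends on q and p, which the SAP does not give, and it fails in one arm of the illustration (47% at q = 0.15). The second holds only if the shell's note on days is ignored.

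The reply does not remove the defect. The SAP still gives two populations for one number. The Table 45 title repeats baseline score 5 or 6, and Section 17 allows the final presentation to differ from the shells. Under the text, the analysis by baseline score would show close to 100% new use in category 6, and the overall figure would remain mixed.

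**Conclusion.** Wrong as written. Section 8.2.12 classes subjects already on NIV/high-flow oxygen as new users, and it contradicts its own term, Sections 8.2.10 and 3.3.5, and the Table 45 shell. Whether the reported figure is affected depends on which of text and shell is programmed.

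If the text is programmed, the risk difference shrinks by (1 − q), given equal s in both arms. Under the assumed inputs the risk ratio moves from 0.75 to 0.87–0.93, and about 47% to 78% of counted cases are existing users. These sizes rest on assumed q and p; the direction does not depend on their values, as long as q is above zero and s is equal in both arms.

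The reach is limited. Section 8.2 describes its results as supportive, Section 6.8 keeps them outside the fixed-sequence tests, and the shell gives a rate difference with a confidence interval and no p-value. The primary analysis and type I error control are unaffected.

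**What to change.** - In Section 8.2.12, restrict the population to subjects with actual baseline ordinal score 5 only, keeping a post-randomization score of 6 as the event.
- In Tables 45 and 46, state that new use and its duration are reported in the block for subjects not on NIV/high-flow oxygen at baseline.
- Summarise baseline-6 subjects only in the block for those on NIV/high-flow oxygen at baseline.

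The cost is a short text edit, a clarifying programming note and a filter in two tables. No new data and no change to any confirmatory analysis are needed.

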8.2.13. Days of Invasive Mechanical Ventilation/ECMO

Duration of Invasive Mechanical Ventilation/ECMO use will be summarized in a table using means, standard deviations, medians, and quartiles by treatment arm ([Table 47](#)). Analyses will be performed in the mITT and As Treated populations and by duration of symptoms at baseline ([Table 48](#)). Bee swarm plots of Invasive Mechanical Ventilation/ECMO days by treatment arm will be generated, where subjects whose days are imputed to the maximum of 28 days due to death are grouped separately from subjects who do not die ([Figure 23](#)).

8.2.14. Incidence of New Invasive Mechanical Ventilation/ECMO

The incidence and duration of new Invasive Mechanical Ventilation/ECMO use will be analyzed by treatment arm. New use will be identified by a post-randomization score of 7. The number of subjects reporting new use and the incidence rate (and CI) will be reported ([Table 47](#)).

8.2.15. Days of Hospitalization

Duration of hospitalization will be summarized in a table using means, standard deviations, medians, and quartiles by treatment arm. Incidence of readmittance will also be summarized ([Table 49](#)). A listing of subjects who were readmitted will be generated ([Listing 29](#)). Analyses will be performed in the mITT and As Treated population and by duration of symptoms at baseline ([Table 50](#)). Bee swarm plots of days hospitalized by treatment arm will be generated, where subjects whose days are imputed to the maximum of 28 days due to death are grouped separately from subjects who do not die ([Figure 24](#)).

8.3. Exploratory Efficacy Analyses

Only Day 60 exploratory outcome measures are covered in this SAP.

8.3.1. Clinical Status Ordinal Scale at Day 60

The number and proportion of subjects along with 95% confidence intervals by category of clinical status will be presented by treatment arm and actual ordinal score for Day 60 ([Table 52](#)). Change from Day 29 to Day 60 will be summarized categorically (e.g., maintained recovery, worsened) at Day 60 ([Table 53](#)).

